The index date (start date of medical record abstraction for the first patient) for the study will be selected for each country and correspond to the date when a site becomes aware of the study objectives. After all approvals from national EC and regulatory authorities have been granted, all medical record data will be retrospectively reviewed until the index date; this approach will ensure the data collected are fully reflective of real world administration of MabThera and not influenced by study awareness. The retrospective review of medical records will occur within a 12-month "look-back" period prior the selected index date (i.e., the eligibility period). The observation period for consenting patients corresponds to the interval between the first and last infusion dates of MabThera, if treatment is discontinued before the index date. If the patient is still on MabThera at the index date, then the observation period is the interval between the first infusion date and index date. Furthermore, if a patient stops and re-starts MabThera during the observation period, all repeated treatment intervals will be captured.

Patient Alert Card survey

The PAC survey will be conducted after the index data and concomitantly with the medical record abstraction process. The PAC survey will be completed once by each patient after informed consent has been provided.

Duration of the study

The planned duration of the study (i.e., both medical record and survey data collection) is approximately 16 months after the recruitment of the first patient. This period takes into account 10 months of data collection and a 6 month period between last patient recruited and final study report.

will closely monitor inclusion rates. If projected recruitment rates indicate that patient targets may not be achieved in the planned recruitment period, consideration will be given to extending the recruitment period, initiating additional sites within the 5 existing countries, and/or expanding the study into additional EU countries.

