8.3 VARIABLES

Medical Record Data

The site will abstract information from the medical record for each of the DUS consenting patients and will enter the abstracted information in an electronic case report form (eCRF):

- Study ID (identification), age, sex
- Condition for which MabThera has been prescribed (via checklist):

- RA
- Ankylosing spondylitis
- Psoriatic arthritis
- Undifferentiated spondyloarthritis
- Juvenile idiopathic arthritis
- SLE
- Systemic vasculitis
- Inflammatory myopathies
- Behçet disease
- Sjögren syndrome
- Nephrotic syndrome
- Reason for MabThera prescription:
 - Failure of previous treatment
 - Adverse events (AEs) under previous treatment
 - Compassionate use
- Date of first diagnosis of the condition
- For patients with RA, severity of RA as measured with the DAS28 (28-joint Disease Activity Score). To calculate the DAS28, the following items will have to be abstracted from the medical record:
 - C-reactive protein level
 - Erythrocyte sedimentation rate
 - Number of tender joints
 - Number of swollen joints
 - Global assessment of patient's general health on the visual analogue scale (VAS) (0–100)
 - Presence of extra-articular involvement
- MabThera dosage for the most recent infusion and number of MabThera infusions in the past 2 years
- Other current and previous anti-inflammatory medication including biological agents other than MabThera
 - Methotrexate (key variable for on- or off-label classification of MabThera use)

- Glomerulonephritis
- Multiple sclerosis/neuromyelitis optica
- Pemphigus vulgaris
- Polydermatomyositis
- Mixed connective tissue disease
- Wegener's GPA/ MPA
- Eosinophilic GPA
- Other (specify)

- Immunosuppressives: prednisolone, glucocorticoid bolus therapy, methylprednisolone, methotrexate, cyclophosphamide, azathioprine, mycophenolate mofetil, intravenous immunoglobulin, plasmapheresis, other immunosuppressives (specify)
- Non-steroidal anti-inflammatory drugs (NSAIDs), including cyclooxigenase (COX)-2 inhibitors
- Biological agents:
 - TNF-alpha inhibitors (key variable for on- or off-label classification of MabThera use): etanercept, infliximab, adalimumab, golimumab, certolizumab pegol, ocrelizumab
 - Interleukin inhibitors: tocilizumab, anakinra
 - Abatacept
 - Janus kinase (JAK) inhibitor: tofacitinib
 - Other biological agents (specify)

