Make sure you have a list of all your medicines when you see a health care professional.

Please talk to your doctor or nurse if you have any questions about the information in this card.

1.	Date of abstraction:	/	(dd/	mm/yyyy)
2.	Date of patient's most recent v	visit to infusion ce (dd/mm/yyyy)	entre:	
3.	Patient's age:			
	 □ 18-25 years □ 26-35 years □ 36-45 years □ 46-55 years □ 56-65 years □ 66-75 years □ 76-85 years □ > 85 years 			
4.	Patient's gender: ☐ Male ☐ Female			
5.	Date of patient's first MabTher (dd/mm/yyyy)	ra infusion:	/	/
6.	Date of patient's most recent I	MabThera infusio (dd/mm/yyyy)	n:	

7.		imary condit Select one a		tient wa	as prescribed MabThe	era:
		Rheumatoi	id arthritis*		Nephrotic syndrome	
		Ankylosing	spondylitis		Glomerulonephritis	
		Psoriatic a	rthritis		Multiple sclerosis/ne	uromyelitis optica
		Undifferent spondyloai			Pemphigus vulgaris	
		Juvenile id arthritis			Polydermatomyositis	;
		Systemic lu			Mixed connective tiss	sue disease
		Systemic v			Wegener's granulom polyangiitis	atosis/microscopic
		Inflammato myopathies			Eosinophilic granulo	matosis with
		Behçet dis	ease		polyangiitis	
		Sjögren sy	ndrome		Other (specify)	
	* C	omplete the S	upplemental Form f	or Patien	nts Receiving MabThera fo	or Rheumatoid Arthritis.
8.	Da	ate of first di	agnosis for prima	ary con	dition:	
		/	/	(dd/m	m/yyyy)	
9.		Failure of p Adverse ev Compassion	ase specify:	nt ious tre		
10.	То	tal number	of MabThera infu	usions i	n the past 2 years:	infusions
11	Ma	abThera dos	sage for most red	cent infi	ısion:	ma

12.	Medications patient has taken within the past 12 months. (Select all that apply.)
	Immunosuppressives
	□ Azathioprine
	☐ Cyclophosphamide
	□ Intravenous immunoglobulin
	☐ Methotrexate
	☐ Methylprednisolone (oral or in bolus)
	☐ Prednisolone (oral or in bolus)
	☐ Glucocorticoid (in bolus)
	☐ Mofetil mycophenolate
	□ Plasmapheresis
	☐ Other immunosuppressive, please specify:
	Non-steroidal anti-inflammatory drugs (NSAIDS)
	□ NSAIDS including COX-2 inhibitors
	Biological agents
	Tumour necrosis factor-alpha inhibitors
	□ Adalimumab
	☐ Certolizumab pegol
	□ Etanercept
	☐ Golimumab
	□ Infliximab
	□ Ocrelizumab
	Interleukin inhibitors
	□ Anakinra
	□ Tocilizumab
	Other biological agents
	□ Abatacept
	☐ Janus kinase inhibitor: Tofacitinib
	☐ Other, please specify:

Medical Record Abstraction Form—Draft

Supplemental Form for Patients Receiving MabThera for Rheumatoid Arthritis

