RA1.	☐ Yes☐ No	•	A1, contin	nue with	RA1	a. If n	o, go to RA2. otrexate use:
		/	/		(dd/n	nm/yy	уу)
RA2.	ever take		ur necrosi	s factor	-alph	a inhi	treatment cycle, did the patient bitors (adalimumab, iximab)?
in time		r to the dat					ts for tests performed closest ion in the patient's current
RA3.	C-reactive	ve protein (CRP) leve	el at first	t Mab	Thera	infusion in the current
	treatmer	nt cycle:		mmol	/L		
	RA3a.	Date of CI	RP test:	/		/	(dd/mm/yyyy)
RA4.	Erythroc	yte sedime	ntation rat	te (ESR) at fi	rst Ma	abThera infusion in the current
	treatmer	nt cycle:	mm/h	r			
	RA4a.	Date of ES	SR:	/	/		(dd/mm/yyyy)

RA5.	Tender j	oint count (0 – 28) at first Mab	Thera infu	ısion in t	he current	treatment
	cycle:	joints				
	RA5a. (dd/mm/	Date of tender joint count:	/	/		
RA6.	Swollen	joint count (0 - 28) at first Mat	Thera inf	usion in	the curren	t treatment
	cycle:	joints				
	RA6a. (dd/mm/	,	/	/		
RA7.		e of extra-articular involvemen reatment cycle:	t at first M	labThera	a infusion i	n the
RA8.		ssessment of patient's genera) at first MabThera infusion in				scale (VAS)
		mm				
	RA8a. (dd/mm/	Date of global health assessr	ment:	/	/	

Medical Record Abstraction Form—Draft

For questions RA9 through RA14a, please provide results for tests performed on or nearest to the date of the patient's most recent MabThera infusion (Q6).

RA9. C-reactive protein (CRP) level at most recent MabThera infusion:

mmol/L Date of CRP test: RA9a. (dd/mm/yyyy) RA10. Erythrocyte sedimentation rate (ESR) at most recent MabThera infusion: mm/hr RA10a. Date of ESR: (dd/mm/yyyy) RA11. Tender joint count (0 - 28) at most recent MabThera infusion: joints RA11a. Date of tender joint count: (dd/mm/yyyy) RA12. Swollen joint count (0 - 28) at most recent MabThera infusion: joints RA12a. Date of swollen joint count: (dd/mm/yyyy) RA13. Presence of extra-articular involvement at most recent MabThera infusion: ☐ Yes □ No

	sessment of patient's general health or at most recent MabThera infusion:	n visu	al ar	nalogu	e scale	(VAS)
	mm					
RA14a. (dd/mm/y	Date of global health assessment:	/		/		

3. Patient Questionnaire - Draft

MabThera Risk Minimisation Programme Evaluation

Patient Questionnaire—Draft

Thank you for agreeing to participate in this study.

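### Form item Q12 is one undated 12-month medication list, so it does not deliver the current and previous treatment that Section 8.3 says is abstracted

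*Protocol*

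**What the plan says.** Section 8.3 (Variables, Medical Record Data) states that sites will abstract "Other current and previous anti-inflammatory medication including biological agents other than MabThera". It sets no time limit and names immunosuppressives, NSAIDs and biological agents. Two entries are singled out: "Methotrexate (key variable for on- or off-label classification of MabThera use") and "TNF-alpha inhibitors (key variable for on- or off-label classification of MabThera use"). The synopsis also names treatment history as a medical-record variable.

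The draft Medical Record Abstraction Form in Appendix 1 implements this as follows:

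- **Q5 and Q6** record the dates of the first and the most recent MabThera infusion.
- **Q9** records the reason for prescription (failure of, or adverse events under, earlier treatment, or compassionate use). It does not name the drug.
- **Q12** is headed "Medications patient has taken within the past 12 months". It is a tick list with no start or stop dates and no column separating current from past use.
- **RA supplement**, completed for RA only: RA1/RA1a cover methotrexate with a date. RA2 asks whether a TNF inhibitor was ever taken, in a question that contains the words "treatment cycle, did the patient". RA3-RA8 record severity at the first infusion of the current cycle, and RA9-RA14 at the most recent infusion.

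Long-term users belong to the sample by design. Under Section 8.1.1, for a patient still on treatment, "the observation period is the interval between the first infusion date and index date". Section 8.6 analyses repeat-infusion and first-infusion patients separately.

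**The concern.** The variable list and the form disagree. Section 8.3 promises current and previous medication; Q12 returns an undifferentiated 12-month list. In a long-term user, those 12 months all fall after MabThera was started. A ticked drug then shows co-medication on MabThera, and whatever preceded MabThera is not recorded.

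Aim 1 is to characterise off-label use as well as to quantify it. What these patients had received before MabThera is a natural part of that description. A field not collected at abstraction cannot be recovered by any later analysis plan, so the mismatch has to be settled on the form.

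**Working it through.** The protocol has no figure to reproduce here. The check compares the two texts and does simple arithmetic on the time window.

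**1. Time before MabThera that Q12 can show.** Let t be the months from first-ever infusion (Q5) to the date from which Q12 counts back. The form does not name that date; I assume the abstraction date (Q1). Then

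visible pre-MabThera months = max(0, 12 − t)

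| t (months since first infusion) | Visible months before MabThera |
|---|---|
| 3 | 12 − 3 = 9 |
| 6 | 12 − 6 = 6 |
| 9 | 12 − 9 = 3 |
| 12 or more | 0 |

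Even where the result is above zero, the list has no dates, so a tick does not show whether the drug came before or after the first infusion.

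**2. Extreme case within the study calendar.** Take a patient first infused at the start of the 12-month look-back and abstracted at the end of the 10-month collection period. Then t = 12 + 10 = 22 and Q12 shows 0 months. If Q12 counts back from the index date instead, t = 12 and the result is again 0. Patients who started before the look-back also show 0 under either reading.

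**3. Who depends on Q12 alone.**

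| Patient group | Items on other medication | Not captured if t is 12 or more |
|---|---|---|
| Off-label conditions | Q12 only | All treatment before MabThera |
| GPA/MPA | Q12 only | All treatment before MabThera |
| RA | Q12, RA1/RA1a, RA2 | Earlier drugs other than methotrexate and TNF inhibitors |

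**4. Number of records.** The protocol gives no share of patients first infused 12 or more months earlier. Assuming 50-80%:

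- of 1,000 records: 0.5 × 1,000 = 500 to 0.8 × 1,000 = 800;
- of 1,500 records: 0.5 × 1,500 = 750 to 0.8 × 1,500 = 1,200.

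These counts include RA patients, whose methotrexate and TNF-inhibitor items sit outside Q12. For off-label patients alone, the Section 8.5 precision example (75% on-label) would leave 0.25 × 1,000 = 250 of 1,000 records. With the same assumed share, 125 to 200 of these would have no pre-MabThera treatment recorded. Both percentages are illustrations, not estimates.

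**5. What does not depend on Q12.** Section 8.3 defines off-label use by disease. Q7 records the condition with no time window, so the main proportion in Section 8.6 can be computed whatever Q12 contains.

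**The case against.** The strongest reply is that the form does more than Q12 suggests, and much of this stands.

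- **The two key drugs have their own RA items.** A reader might infer that all medication history is cut at 12 months, or that TNF-inhibitor history is limited to the current cycle. The form does not support that. RA2 asks about TNF inhibitors ever taken, and RA1/RA1a cover methotrexate with a date.
- **TNF use between cycles.** A reader might also infer that a TNF inhibitor taken between two MabThera cycles would be miscounted as prior use. The opening words of RA1 and RA2 are broken in the text available, so the exact reference point of RA2 cannot be read and this is unproven.
- **Severity timing contradicts nothing.** Section 8.3 asks for "For patients with RA, severity of RA as measured with the DAS28" and fixes no time point. For patients in a second or later cycle, no pre-MabThera DAS28 is captured. However, anchoring on the current cycle is a coherent choice, and moving RA3-RA8 to the first-ever infusion would delete severity at the start of the current cycle.
- **The reason for prescription is recorded.** Q9 has no 12-month limit, so why MabThera was given is not lost. What is missing is which treatment failed or was not tolerated.
- **Previous need not mean before MabThera.** A drug stopped eight months ago is previous and would be ticked. That is fair, but the undated list cannot show that it was stopped, and drugs stopped more than 12 months ago do not appear.
- **The form is a draft with a planned pilot.** This makes the change easy; it does not remove the mismatch.

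**Conclusion.** The concern holds in a limited form. Q12 does not deliver the medication scope stated in Section 8.3. It cannot separate current from previous drugs, and for anyone first infused 12 or more months before its reference date it shows no treatment before MabThera. The gap is complete for non-RA patients; in RA it is confined to drugs other than TNF inhibitors and methotrexate.

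The consequence is a loss in describing treatment history under aim 1. A reader might infer that patients would be misclassified as on- or off-label. The documents do not support this for the main estimate, which rests on disease alone. Section 8.6 also mentions strict and broad on-label use, but the protocol defines neither term, so no dependence on Q12 can be shown.

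The mechanism follows from the text and needs only the assumption about where the 12 months end; both readings checked give the same answer for long-term users. The record counts rest on an assumed 50-80% share and should be read only as an order of size.

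**What to change.** Before the pilot of the abstraction form, split each Q12 entry into two columns: taken at any time before the first MabThera infusion (date in Q5), and being taken at the most recent infusion (date in Q6). Both dates are already on the form. Use the data-not-available answer that Section 8.3 already provides where old records cannot be found. Leave RA3-RA14 as they are.

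The cost is somewhat more abstraction time and more unavailable answers for long-term users. A drug started after the first infusion and stopped before the most recent one would fall in neither column; if it matters, keep the 12-month tick as a third column.

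If the sponsor prefers the 12-month list, the minimum is to narrow Section 8.3 to what Q12 collects, state the date from which the 12 months count back, and acknowledge that treatment before MabThera will not be described for long-term users outside RA1 and RA2.

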A "data not available" response will be available where appropriate for those record abstraction items for which data may be missing from patient records. This type of response will help reduce missing data and will document the overall gaps in record keeping.

A brief pilot test of the translated version of the abstraction form will be conducted in each country, and the abstraction form in one or more countries may be adjusted based on the results of this pilot.

A draft version of the medical record abstraction form is included with this document (Appendix 1).

Off-Label Use Definition

The definition of off-label use of MabThera will be based on the use for a non-oncology disease or medical condition other than RA and GPA/MPA covered by MabThera SPC.

In absence of labelled indications, potential off-label use could include, but is not limited to, the following conditions:

- Ankylosing spondylitis
- Psoriatic arthritis
- Undifferentiated spondyloarthritis
- Juvenile idiopathic arthritis
- SLE
- Systemic vasculitis

- Eosinophilic GPA
- Inflammatory myopathies
- Behçet disease
- Sjögren syndrome
- Nephrotic syndrome
- Glomerulonephritis
- Multiple sclerosis/neuromyelitis optica
- · Pemphigus vulgaris
- Polydermatomyositis
- · Mixed connective tissue disease

Patient Survey data

The patient questionnaire has been developed following standard survey methodological principles and will be cognitively tested with patients in each of the target countries. Modifications will be made to the questionnaire based on the results of testing, and some variations to the questionnaire are anticipated based on country-specific requirements.

The questionnaire will include an introductory section with questions to confirm eligibility. The majority of the questionnaire items will be closed ended, ensuring that the resulting data are easy to analyse and interpret. Closed-ended questions are generally more efficient than open-ended questions (or open-ended text fields) and more conducive to summarisation and statistical analyses.

The questionnaire will collect the following information (please refer to Appendix 1 for the draft questionnaire):

- Demographics (e.g., age, sex, ethnicity)
- Patient previous history of PML or other serious infectious diseases
- Whether the patient has received a previous treatment with MabThera, if so, number of prior infusions during the last 12 months
- Patient understanding or awareness of the following:

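### The abstraction form lets DAS28 components measured after the most recent infusion stand as the value at that infusion, unlike the first-infusion block, and the displaced earlier value is not recorded

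*Protocol*

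**What the plan says.** Section 8.3 of the protocol makes the DAS28 the measure of severity in rheumatoid arthritis and introduces its inputs with "To calculate the DAS28, the following items will have to be abstracted from the medical record". The list that follows ends with "Presence of extra-articular involvement". The section names no time point for the score.

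The supplemental rheumatoid arthritis form in Appendix 1 then collects the items in two blocks.

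- **First infusion of the current treatment cycle (RA3 to RA8a).** Sites give results for "tests performed closest" in time to that infusion. The next words are damaged in the available text. The surviving fragment is consistent with *prior to the date*.
- **Most recent infusion (RA9 to RA14a).** The instruction is "For questions RA9 through RA14a, please provide results for tests performed on or nearest to the date of the patient's" most recent infusion. Results from either side qualify, at any distance.

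Each block has room for one result per component. Every DAS28 component has its own date field, for example "RA10a. Date of ESR" and "RA11a. Date of tender joint count". Extra-articular involvement (RA7 and RA13) is a yes/no item with no date field.

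**The concern.** The second block is worded as the patient's state at the most recent infusion. A result obtained weeks later can reflect the effect of that infusion, so recording it as the value at the infusion would tend to make the disease look milder, most of all in patients who respond.

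Aim 1 is to characterise the disease of treated patients, and Section 6.2 gives the label as severe, active disease. Severity is therefore part of what this component reports. If the two blocks follow different timing rules, a comparison of first with most recent infusion also partly compares the rules.

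**Working it through.** The protocol gives no DAS28 formula, no component distributions and no visit intervals. The main check is therefore of the text, followed by an illustration on assumed inputs.

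**1. The two instructions compared**

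| | First infusion of cycle (RA3–RA8a) | Most recent infusion (RA9–RA14a) |
|---|---|---|
| Which result | closest in time | on the date or nearest to it |
| Direction | before the infusion, as far as the text can be read | none |
| Maximum distance | none | none |
| Results per component | one | one |
| Component dated | yes | yes |

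The difference in direction shows most clearly in a patient whose current cycle has only one infusion. The first and the most recent infusion are then the same event, yet the two blocks can hold different values for it.

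**2. Can later results be in the record?** Yes. Section 8.1.1 has records reviewed up to the index date, with a 12-month look-back. If the most recent infusion came some time before the index date, tests from the interval between them can be in the chart. The index date limits how late a result can be but does not exclude it.

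**3. What is lost.** Assume joint counts 8 weeks before and 6 weeks after the infusion, and a single ESR 10 weeks before it.

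- Current rule: 6 < 8, so the later joint count is recorded. The ESR and the joint count are then 10 + 6 = 16 weeks apart, on opposite sides of the infusion.
- Closest on or before: the count at 8 weeks is recorded. The gap is 10 − 8 = 2 weeks, and both results precede the infusion.

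Under the current rule the date field shows that the joint count is late, so an analyst can drop it. The count at 8 weeks is not in the database. Section 2 keeps medical records at the centre, so recovering it would mean returning to the site. The query process in Sections 8.7.1 and 8.7.2 deals with discrepant data, and a form completed as instructed is not discrepant.

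**4. Illustration of size (all inputs assumed).** The formula, which is not in the protocol, is DAS28-ESR = 0.56√(tender) + 0.28√(swollen) + 0.70 ln(ESR) + 0.014 × global.

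- All components before infusion (tender 10, swollen 8, ESR 40, global 60): 1.771 + 0.792 + 2.582 + 0.840 = 5.99.
- Same ESR, the rest after infusion (5, 3, 40): 1.252 + 0.485 + 2.582 + 0.560 = 4.88.

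The unrounded difference is 1.11. By component:

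| Taken after infusion | Fall in score |
|---|---|
| none | 0 |
| global only | 0.840 − 0.560 = 0.28 |
| swollen joints only | 0.792 − 0.485 = 0.31 |
| tender joints only | 1.771 − 1.252 = 0.52 |
| all three | 1.11 |

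**5. Extra-articular involvement.** It has no term in the formula assumed above. The form also treats it apart from the components, as an undated yes/no item. Its place in the Section 8.3 list is a drafting error.

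**The case against.** The case for leaving this alone is substantial, and much of it stands.

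- **Severity before the current cycle is already captured.** RA3 to RA8a appears to hold it. A reader might infer that severity at the treatment decision is lost, but the documents do not support that. For patients with repeat infusions, values on both sides of the most recent one are already on treatment, so the contrast is before and after that infusion and not before and after treatment.
- **Mixing is possible, not certain.** A reader might infer that the score describes no single time point. However, the instruction puts the infusion date first, and components measured at one visit give one time point. Nothing in the protocol shows how often dates differ, and nothing obliges anyone to combine results from different dates into one score.
- **A window or same-visit rule can sit in the analysis plan.** The components are dated, and Section 8.6 defers detailed methods to that plan. The absence of such a rule here is no defect.
- **The main result is untouched.** Section 8.3 defines off-label use by disease. Section 8.6 also mentions strict and broad on-label use, but the protocol does not say that DAS28 enters either.
- **The form is a draft.** Section 8.3 plans a pilot that may adjust it.

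One part survives. An analysis rule can act only on values that were abstracted, and the instruction decides which value that is. The planned pilot makes this a convenient time for the change.

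**Conclusion.** The point holds in a limited form, as a cheap improvement to a secondary descriptive variable. The RA9 to RA14a instruction allows a result from after the most recent infusion to be recorded as the value at it, and the displaced earlier result is not kept. Severity at that infusion may therefore be understated, and the two blocks are not on the same footing.

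The understatement assumes that some patients have later tests in the record that lie nearer than the earlier ones, and that these show improvement. Its size is unknown. The range of 0 to 1.11 points is for one assumed patient; it is not an estimate for the study, and the protocol sets no severity cut-off against which to judge it. The contrast between the blocks rests on reading the damaged RA3 to RA8 instruction as *prior to*. If that reading is wrong, both blocks share the problem.

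**What to change.** - In the instruction above RA9, ask for the closest result on or before the date of the most recent infusion. Check the wording above RA3 in the source file and give both blocks the same direction.
- Use the component dates already on the form to flag scores whose components come from different visits. The tolerance can be set in the analysis plan.
- In Section 8.3, move extra-articular involvement out of the list of items for calculating the DAS28 and list it as a separate severity item, as RA7 and RA13 already do.

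The cost is one line on the form, one moved bullet and a derivation flag, with no new data fields. The downside is that some component values will be older, or will fall under the existing response for data that are not available. In those patients the remaining components can still be tabulated singly.
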